### 3. OBJECTIVES

#### 3.1. Primary objective

- To assess the persistence of anti-hepatitis A virus (HAV) antibodies, *approximately* 8 years and 10 years post vaccination with the last received vaccine dose of the complete series of *Havrix* (2 doses) and the partial series completion (1 dose) in Panama.

#### 3.2. Secondary objectives

- To assess geometric mean concentration (GMC) of anti-HAV antibodies, *approximately* 8 years and 10 years post vaccination with the last received dose of the complete series of *Havrix* (2 doses) and the partial series completion (1 dose) in Panama.
- To explore the non-inferiority of the 1-dose schedule of *Havrix* when compared to the 2-dose schedule in terms of the percentage of subjects with anti-HAV antibody concentrations  $\geq 15$  mIU/mL, *approximately* 8 years and 10 years after the last received vaccination dose.

*Criteria for evaluation: The lower limit of the 2-sided 95% CI for the difference (1-dose group minus the 2-dose group) of percentage of subjects with anti-HAV antibody concentrations  $\geq 15$  mIU/mL is greater than or equal to the pre-defined clinical non-inferiority limit of -10%.*

### 4. ENDPOINTS

#### 4.1. Primary endpoint

- Anti-HAV seropositivity status at *approximately* 8 years and 10 years after administration of the last dose of *Havrix*.

*Subjects are defined as being seropositive if their anti-HAV antibody concentration is  $\geq 15$  mIU/mL.*

## 4.2. Secondary endpoints

- Anti-HAV concentrations (GMC) at **approximately** 8 years and 10 years after administration of the last dose of *Havrix*.
- Anti-HAV seropositivity status at **approximately** 8 years and 10 years after administration of the last dose of *Havrix* – corresponds to the secondary objective for non-inferiority.

*Subjects are defined as being seropositive if their anti-HAV antibody concentration is  $\geq 15 \text{ mIU/mL}$ .*

## 5. STUDY POPULATION

The list of applicable elimination codes for each cohort can be found in the study specific form FORM-BIO-CLIN-9004-05 Criteria for eliminating subjects from the analyses.

Cohort	Elimination codes	Eli Type
Total enrolled cohort at Year 8 (Epoch 1)	900	Y8
ATP cohort for analysis for persistence at Year 8 (Epoch 1)	2010, 2100, 2120	Y8
Total enrolled cohort at Year 10 (Epoch 2)	900	Y10
ATP cohort for analysis for persistence at Year 10 (Epoch 2)	2010, 2100, 2120	Y10

## 6. STATISTICAL METHODS

All statistical analyses will be performed using SAS version 9.3 or later.

### 6.1. Analysis of demographics/baseline characteristics

All the analyses concerning objectives will be performed on the ATP cohort for each cross-sectional survey (Epoch1, Epoch2).

#### *Demography*

The number of subjects enrolled as well as the number excluded from the ATP analysis will be presented.

The distribution of subjects by centre will be tabulated according to *Havrix* dose group.

Demographic characteristics such as age at the Persistence visit, age/age class [months] at the time of first and second dose of *Havrix* administration, time interval [months] between *Havrix* dose 1 and dose 2 administration, time since last *Havrix* dose [years], sex, geographic ancestry, rural and urban residency of the subjects will be summarized using descriptive statistics per dose group and overall:

- Frequency tables will be generated for categorical variables such as sex.
- Mean, median, standard deviation, minimum and maximum will be provided for continuous data such as age.

The analysis will be performed on the Total enrolled and ATP cohorts for the demographic part.

***Subjects enrolled in the two epochs***

The number and percentage of subjects enrolled in the two epochs will be summarised once the 2 surveys have been completed at Epoch 2, by *Havrix* dose group.

***Hepatitis A infection disease history***

The percentage of subjects with a history of Hepatitis A infection will be tabulated, the age at the infection [years] and the time between the infection and the last *Havrix* dose [year].

***General medical history***

The percentage of subjects reporting any pre-existing conditions, signs or symptoms having started before enrollment in the study will be summarized by diagnosis status, current or past.

## **6.2. Analysis of persistence**

If the percentage of enrolled subjects with available serological results excluded from the ATP cohort is more than 5%, a sensitivity analysis based on the Total enrolled cohort will be performed.

***Within group analysis***

For the subjects who had received either one dose or two doses of *Havrix*, at each serosurvey (**approximately** 8 years and 10 years after the last vaccine dose):

- Percentage of subjects with concentrations above the cut-off ( $\geq 15\text{mIU/mL}$ ) with exact 95% CI will be calculated [seropositivity rate].
- Geometric mean concentration (GMC) with 95% CI will be tabulated.
- The distribution of antibody concentrations will be presented by histogram of anti-HAV log titer and also using reverse cumulative curves.

The seropositivity rate and the geometric mean concentrations (GMC) with 95% Confidence Intervals (CI) of antibody to hepatitis A virus (Anti-HAV) will be calculated and presented overall, by *Havrix* dose group, by follow up time class period after their last *Havrix* vaccination dose and by age class at the first *Havrix* dose.

***Between groups analysis:***

An evaluation of the differences in the immune response **approximately** 8 years and 10 years after the last vaccination dose with *Havrix* between the subjects who received only one dose of *Havrix* and subjects who received two doses of *Havrix* will be performed in terms of:

- Differences in seropositivity rate (seropositive = *anti-HAV antibody concentrations above the cut-off ( $\geq 15\text{ mIU/mL}$ )*) between the subjects who received only one dose of *Havrix* and subjects who received two doses of *Havrix* at each serosurvey.

Computation of the asymptotic standardised 2-sided 95% CIs for the difference in the percentage of subjects with anti-HAV antibody concentrations  $\geq 15\text{ mIU/mL}$  at

Year 8 or at Year 10 after the last received *Havrix* vaccination dose (1-dose group minus the 2-doses group). If the lower limit of the 2-sided 95% CI for the difference (1-dose group minus the 2-doses group) is greater than or equal to the pre-defined clinical limit of -10%, non-inferiority of 1 dose will be demonstrated.

- Ratio (1-dose group/2-doses group) of the anti-HAV GMCs between the subjects who received only one dose of *Havrix* and subjects who received two doses of *Havrix* with their 95% CI at each serosurvey.

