8.2. Determination of sample size

The primary objective of this study is to evaluate the persistence of anti-HAV antibodies, approximately 8 years and 10 years post vaccination with the last vaccination of the complete series of *Havrix* (2 doses) and the partial series (1 dose). Around 300 subjects will be enrolled in each group at Year 8 and Year 10 visits. Considering that 10-15% of the subjects will be non-evaluable or will not have any available immunogenicity result, it will be assumed that around 260 subjects per group will be included in the ATP cohort of persistence at Year 8 and at Year 10 for the analysis of the primary endpoint.

Table 9 illustrates the accuracy that can be expected from sample size of 260 evaluable subjects in each group at Year 8 and Year 10 visits for evaluating the percentage of subjects with anti-HAV concentrations ≥ 15 mIU/mL. With 260 subjects per group, the width of the 95% CI giving a precision of approximately 5% around the point estimate is considered meaningful.

Table 9 Exact 95% confidence intervals of the percentage of subjects with anti-HAV concentrations greater than or equal to 15 mIU/mL

	Percentage (%)	N=260
At Year 8 and Year 10	20	[15.3; 25.4]
	30	[24.5; 36.0]
	40	[34.0; 46.2]
	50	[43.8; 56.2]
	60	[53.8; 66.0]
	70	[64.0; 75.5]
	80	[74.6; 84.7]
	90	[85.7; 93.4]
	100	[98.6; 100.0]

N: Total number of eligible subjects with available immunogenicity results

Table 10 illustrates the sample size and the power associated with the objective below at each epoch. The power to meet the criteria associated the objective below is at least 80% with 260 evaluable subjects in each group at each cross-sectional survey time period (Year 8 and Year 10 visits).

In terms of seropositivity rates: To explore the non-inferiority of the 1-dose of *Havrix* when compared to 2-doses in terms of the percentage of subjects with anti-HAV antibody concentrations ≥ 15 mIU/mL, approximately 8 years and 10 years after the last vaccination dose.

Criteria for evaluation: *The lower limit of the 2-sided 95% CI for the difference (1-dose group minus the 2-dose group) of percentage of subjects with anti-HAV antibody concentrations ≥ 15 mIU/mL is greater than or equal to the pre-defined clinical non-inferiority limit of -10%.*

Table 10 Power to show non-inferiority of the immunogenicity of 1-dose compared to 2-doses of Havrix

Endpoint	% in the two group**	δ	Power* N=260/group
Anti-HAV \geq 15 mIU/mL	80%	-10%	80.9%

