* Pass 2005, one-sided equivalence test of proportions (non-inferiority), alpha = 2.5%, power under equal proportions.

H0: group difference in expected % of subjects with anti-HAV concentrations $< \delta$ (P1-dose – P2-dose $< -10\%$)

Ha: group difference in expected % of subjects with anti-HAV concentrations $\geq \delta$ (P1-dose – P2-dose $\geq -10\%$)

**References used for the sample size calculation: [Racznik, 2013 and Hammitt, 2008]

8.3. Cohorts for Analyses at Years 8 and 10

The following cohorts will be defined separately for each epoch.

8.3.1. Total cohort at Year 8 or Year 10

The total cohort at Year 8 or at Year 10 will include all subjects enrolled in the study at Year 8 or Year 10 serosurveys, respectively. For the analysis of persistence, this will include subjects for whom data concerning persistence endpoint measures are available.

8.3.2. Total effective cohort at Year 8 or Year 10

The total effective cohort at Year 8 or Year 10 will include all enrolled subjects who have a valid ICF at Year 8 or Year 10 serosurveys, respectively.

8.3.3. According-to-Protocol (ATP) cohort for persistence at Years 8 or 10 (Amended: 24 July 2017)

The ATP cohort for persistence at Year 8 or at Year 10 will include all enrolled subjects:

- who have a valid ICF
- who have available assay results at Year 8 or Year 10 serosurveys, respectively.
- who have not received a hepatitis A vaccine other than Havrix.
- who do not have a history hepatitis A infection prior to study.
- who have available HAV vaccination records.
- who received either 1 or two doses of Havrix at selected health centres of Panama.
- who have ≥ 7 years and < 10 years between last dose and Persistence Visit 1 (Year 8) and children ≥ 10 years and < 13 years between last dose and Persistence Visit 1' (Year 10).

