8.6. Analysis of primary and secondary objectives

All statistical analyses will be performed using statistical analysis system version 9.2 or later. All the analyses will be described in detail in the statistical analysis plan (SAP).

The analysis for persistence at Year 8 and at Year 10 serosurveys will be based on the ATP cohort. If the percentage of enrolled subjects with available serological results excluded from this ATP cohort is more than 5%, a second analysis based on the Total effective cohort will be performed to support the ATP analysis.

Analysis of persistence

For the subjects who had received either one dose or two doses of *Havrix*, at each serosurvey (approximately 8 years and 10 years after the last vaccine dose):

- Percentage of subjects with concentrations above the proposed cut-off with exact 95% CI will be calculated.
- GMCs with 95% CI will be tabulated.
- The distribution of antibody concentrations will be tabulated and also presented using reverse cumulative curves.

Exploratory between groups analysis:

An exploratory evaluation of the differences in the immune response approximately 8 years and 10 years after the last vaccination dose with *Havrix* between the subjects who received only one dose of *Havrix* and subjects who received two doses of *Havrix* at each serosurvey (approximately 8 years and 10 years after the last received vaccine dose) will be performed in terms of:

- Differences in anti-HAV antibody concentrations between the subjects who received only one dose of *Havrix* and subjects who received two doses of *Havrix* at each serosurvey.

Computation of the asymptotic standardised 2-sided 95% CIs for the difference in the percentage of subjects with anti-HAV antibody concentrations ≥ 15 mIU/mL at Year 8 or at Year 10 after the last received *Havrix* vaccination dose (1-dose group minus the 2-dose group): if the lower limit of the 2-sided 95% CI for the difference in the percentage of subjects with anti-HAV antibody concentrations ≥ 15 mIU/mL at Year 8 or at Year 10 serosurveys, (1-dose group minus the 2-dose group) is greater than or equal to the pre-defined clinical limit of -10%, the pre-defined criteria for the exploratory objective is considered met and the 1-dose group non-inferior to the 2-dose group in terms of seropositivity rate).

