8.7. Interpretation of analyses

All the analyses will be descriptive with the aim to characterise the immunogenicity within and between study groups. Because of the exploratory nature of the comparisons no conclusions can be made.

There will be no comparison between the two serosurveys (Year 8 and Year 10). It will be descriptive in nature.

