### 8.2. Statistical considerations for interim analyses

No interim analysis is planned. However the analysis will be done separately for the two epochs. As all analyses are descriptive, no adjustment of type I error is needed.

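### SAP 6.2 says that meeting the -10% limit demonstrates non-inferiority of one dose, but Protocol 8.7 allows no conclusion from this exploratory comparison

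*SAP*

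**What the plan says.** SAP 6.2, between groups analysis, takes the difference in seropositivity (one dose minus two doses) with a two-sided 95% confidence interval at each survey. If the lower limit is at or above -10%, the SAP says that "non-inferiority of 1 dose will be demonstrated".

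Protocol 8.7, the section on interpretation, states: "All the analyses will be descriptive with the aim to characterise the immunogenicity within and between study groups". It continues: "Because of the exploratory nature of the comparisons no conclusions can be made".

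Protocol 8.6 describes the same comparison under a heading that calls it exploratory. When the limit is met, it says, "the pre-defined criteria for the exploratory objective is considered met and the 1-dose group non-inferior to the 2-dose group".

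Elsewhere the SAP keeps the cautious status. Its secondary objective in 3.2 begins "To explore the non-inferiority of the 1-dose schedule of" and goes on to name the vaccine. SAP 8.2 says: "As all analyses are descriptive, no adjustment of type I error is needed". Protocol 8.8.2 makes the same statement.

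**The concern.** To say that non-inferiority has been demonstrated is to draw a conclusion. Protocol 8.7 covers comparisons between groups and says that none can be drawn. Both statements are current text, and the SAP's document history ties it to Protocol Amendment 2, which contains 8.7. The two cannot both govern the same result.

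What is at stake is the claim that the report may make. Protocol 1.1 presents a one-dose series as a possible answer for Latin American countries with limited resources, and says that evidence on its long-term protection is limited, so a statement of demonstrated non-inferiority would find an audience. SAP 8.1 designates the Year 8 analysis for the trial registry and the Year 10 analysis for the study report, so the wording could appear in two places.

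The caution in 8.7 also fits the design. Under Protocol 6.5.7, children are placed in a dose group from their past vaccination history, and SAP 7.1 gives no adjustment for the difference in proportions.

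**Working it through.** **1. The plan's own figure.** The only figure attached to this comparison is the power in Protocol 8.2, Table 10: 80.9% with 260 evaluable children per group, 80% seropositive in both groups, a margin of -10% and one-sided alpha of 2.5%. I checked it with the score test that uses the variance restricted to the null hypothesis.

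- Standard error under the alternative: √(2 × 0.80 × 0.20 / 260) = 0.03508.
- Restricted estimates under a difference of -0.10: 0.8411 (two doses) and 0.7411 (one dose).
- Restricted standard error: √((0.8411 × 0.1589 + 0.7411 × 0.2589) / 260) = 0.03539.
- Power: Φ((0.10 − 1.96 × 0.03539) / 0.03508) = Φ(0.873) = 80.9% (80.88% before rounding).

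The stated power reproduces, so the calculation is not in question.

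**2. The statements side by side.**

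| Place | Status given to the comparison | What follows if the limit is met |
|---|---|---|
| Protocol 3.2; SAP 3.2 | To be explored | Criterion given, no claim attached |
| Protocol 4.1 | Preliminary data | Not stated |
| Protocol 8.6 | Exploratory | Exploratory criterion met, and one dose called non-inferior |
| Protocol 8.7 | Descriptive and exploratory | No conclusion allowed |
| Protocol 8.8.2; SAP 8.2 | Descriptive, hence no type I error adjustment | Not stated |
| SAP 6.2 | No label | Non-inferiority demonstrated |

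**3. What differs.** The margin, the interval and the criterion for the seropositivity difference are the same in Protocol 8.6 and SAP 6.2. The label and the consequence differ. Protocol 8.6 uses the word exploratory in the heading, in the opening sentence and in the decision sentence. SAP 6.2 omits it in all three places and ends in a demonstration.

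**4. Whether any text resolves it.** SAP section 9, on changes from planned analyses, does not list a change of status. The SAP does not repeat the no-conclusions sentence of Protocol 8.7. Neither document says that one prevails over the other. Protocol 8.8 requires departures from the protocol's plan to be described and justified in the final report, but it does not say what status the result has when the limit is met.

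**5. The SAP against itself.** SAP 8.2 gives descriptive status as its reason for making no adjustment. A rule in 6.2 that demonstrates non-inferiority is not descriptive, so it removes the reason on which 8.2 relies.

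**The case against.** The strongest defence has three parts. First, the tension begins in the protocol: 8.6 already calls the one-dose group non-inferior before 8.7 bars conclusions, so the SAP only shortens and hardens existing wording. Second, exploratory status is stated so often (Protocol 3.2, 4.1, 8.2, 8.6, 8.7 and 8.8.2; SAP 3.2 and 8.2) that an informed reader would hardly be misled by one sentence. Third, Protocol 8.8 obliges the final report to explain any departure.

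Much of this stands. The fault is shared between the documents, and it is an inconsistency of wording. It does not remove the point. SAP 6.2 is where the analyst finds the decision rule, and there the qualifier is missing and the consequence is strongest. Disclosing a departure afterwards does not settle which claim is permitted.

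A reader might infer three stronger things that the documents do not support.

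- *That the sample size section already makes the test confirmatory.* The Table 10 title reads "Power to show non-inferiority of the immunogenicity of 1-dose compared to 2-doses of Havrix" and its footnote "one-sided equivalence test of proportions (non-inferiority), alpha = 2.5%, power under equal proportions". But Protocol 8.2 states the powered objective as one to be explored. Giving power, hypotheses and an alpha for an exploratory criterion contradicts nothing, so I do not count this section as part of the conflict.
- *That two unadjusted surveys inflate the rate of false claims.* That would need a rule under which success at either survey supports one general claim, and no such rule is written. SAP 6.2 evaluates each survey, and both documents analyse the two epochs separately. The full inflation would also need a true difference of exactly -10 points in both surveys.
- *That the SAP has turned the study into a confirmatory trial.* The objective, margin, interval and criterion are unchanged, and the SAP still calls all its analyses descriptive.

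**Conclusion.** The inconsistency is real and should be corrected. SAP 6.2 attaches to the -10% criterion a conclusion that Protocol 8.7 excludes and that SAP 3.2 and 8.2 do not support. Protocol 8.6 carries a milder form of the same tension.

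Its numerical size is nil: no estimate, confidence interval, power or sample size changes, and the primary objective (seropositivity with exact intervals in each group) is untouched. What changes is the claim that may be made when the criterion is met.

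This rests on reading *demonstrated* as a conclusion in the sense of Protocol 8.7, and on the absence of any statement that one document overrides the other. It does not rest on any error-rate calculation.

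**What to change.** To keep the status that Protocol 8.7 gives:

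- Head the SAP 6.2 analysis *Exploratory between groups analysis*, as Protocol 8.6 does.
- Replace the sentence on demonstration with: *the pre-defined exploratory criterion is considered met at that survey; no confirmatory conclusion of non-inferiority will be drawn (Protocol 8.7)*.
- Align the non-inferior wording in Protocol 8.6 with 8.7 at the next amendment. Until then, note in SAP section 9 that it is read subject to 8.7.

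The cost is a heading, a sentence and a note. The downside is a weaker claim, which is the one Protocol 8.7 already allows.

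If the sponsor instead intends a confirmatory claim, editing SAP 6.2 alone is not enough. Before the data are analysed, every exploratory, descriptive or preliminary statement must be revised: Protocol 3.2, 4.1, 8.2, 8.6, 8.7 and 8.8.2, the matching synopsis text, and SAP 3.2 and 8.2. The revision must say whether the claim is made per survey or across both. That needs a protocol amendment as well as a SAP revision. The choice is the sponsor's, but SAP 6.2 and Protocol 8.7 must agree.

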### **6.3. Analysis of safety**

SAEs related to study procedures reported during the entire study will be listed.

## **7. STATISTICAL CALCULATIONS**

### **7.1. Methods for calculating Confidence Intervals (CIs),**

All CI's will be 2-sided 95% CI.

- The exact 95% CIs for a proportion within a group will be calculated [[Clopper, 1934](#)].
- The standardized asymptotic 95% CI for the group difference in proportions will be calculated [[Robert, 1998](#)]: the standardized asymptotic method used within GSK Vaccine is **method 6**
- The 95% CI for Geometric mean concentrations (GMCs) will be obtained within each group separately. The 95% CI for the mean of log-transformed concentrations will be first obtained assuming that log-transformed values were normally distributed with unknown variance. The 95% CI for the GMCs will be then obtained by exponential-transformation of the 95% CI for the mean of log-transformed concentrations.
- The GMC ratio will be obtained using an ANOVA model on the logarithm based 10-transformed concentrations. The ANOVA model will include the dose group as fixed effect. The GMC ratio and its 95% CI will be derived as exponential-transformation of the log-transformed mean difference and its 95% CI.

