3.2. Secondary objectives

- To assess geometric mean concentration (GMC) of anti-HAV antibodies, approximately 8 years and 10 years post vaccination with the last received dose of the complete series of *Havrix* (2 doses) and the partial series completion (1 dose) in Panama.
- To explore the non-inferiority of the 1-dose schedule of *Havrix* when compared to the 2-dose schedule in terms of the percentage of subjects with anti-HAV antibody concentrations ≥ 15 mIU/mL, approximately 8 years and 10 years after the last received vaccination dose.

Criteria for evaluation: The lower limit of the 2-sided 95% CI for the difference (1-dose group minus the 2-dose group) of percentage of subjects with anti-HAV antibody concentrations ≥ 15 mIU/mL is greater than or equal to the pre-defined clinical non-inferiority limit of -10%.

Refer to Section 8.1.2 for the definition of the secondary endpoints.

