6.5.5. Collect socio-demographic data

Record demographic data such as date of birth, gender, geographic ancestry, urban or rural residency in the subject's eCRF.

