- Ratio of the anti-HAV GMCs between the subjects who received only one dose of *Havrix* and subjects who received two doses of *Havrix* with their standardised asymptotic 95% CI at each serosurvey.

Computation of the GMC ratio and its 95% CI:

For all analyses (exploration evaluation of differences between groups), the GMC ratio and its 95% CI will be computed using an analysis of variance (ANOVA) model on the log10-transformed concentration with the group and area of residence as fixed effects in the model.

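### The seropositivity difference set against -10% ignores area of residence, and the SAP also drops residence from the GMC model; any resulting bias could run in either direction

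*SAP*

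**What the plan says.** **The criterion.** Protocol 3.2 requires the lower 95% limit for the seropositivity difference (1 dose minus 2 doses) to be "greater than or equal to the pre-defined clinical non-inferiority limit of -10" percentage points. SAP 6.2 repeats the rule ("If the lower limit of the 2-sided 95% CI for the difference (1-dose group minus the 2-doses group) is greater than or equal to" the same limit) and says that meeting it demonstrates non-inferiority.

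**The method.** SAP 7.1 reads "The standardized asymptotic 95% CI for the group difference in proportions will be calculated", using method 6 of its cited comparison of intervals. Protocol 8.6 specifies the same kind of interval. Neither has a stratum or covariate.

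**Residence.** Protocol 6.5.5 records "geographic ancestry, urban or rural residency in the" eCRF. Protocol 8.6 obtains the GMC ratio from an ANOVA "model on the log10-transformed concentration with the group and area of residence as fixed effects in the model". SAP 7.1 fits that ANOVA with dose group as the only fixed effect, and SAP section 9 does not mention the removal. SAP 6.2 breaks seropositivity down by dose group, follow-up time and age class at first dose, but not by residence.

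**Group formation.** Protocol 6.5.7 assigns children from their recorded doses and dates. SBIR only counts enrolment per group and closes a group when it is full (protocol 5.1 and 6.5.6).

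**The concern.** A child is in the 1-dose group because no second dose was recorded. Whatever led to that may be associated with where the child lives. The endpoint is any anti-HAV concentration of at least 15 mIU/mL, from whatever source, so naturally acquired antibody counts as persistence. If exposure also differs by residence, a crude comparison mixes the effect of schedule with the effect of place.

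The protocol accepts residence as a between-group covariate, but only for the GMC ratio, which has no decision rule. The proportion that does have one is left crude, and the SAP then removes residence from the GMC model too. At stake is whether a lower limit above or below -10 points reflects the schedules or the mix of children in each group.

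**Working it through.** **Inputs from the documents**
- Protocol 8.2, Table 10: 80% in both groups, margin -10 points, stated power 80.9%.
- Test, from its footnote: "one-sided equivalence test of proportions (non-inferiority), alpha = 2.5%, power under equal proportions".
- Size: "The power to meet the criteria associated the objective below is at least 80% with 260 evaluable subjects in each group". This comes from 300 enrolled, "Considering that 10-15% of the subjects will be non-evaluable or will not have any available immunogenicity result": 300 x 0.85 = 255 to 300 x 0.90 = 270, taken as 260.

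**Inputs not in the documents, so assumed**
- Difference between dose groups in the share living in the higher-seropositivity area: 10 to 30 points.
- Seropositivity gap between areas at the same number of doses: 5 to 15 points, equal in both dose groups.
- Area of residence in protocol 8.6 means the urban/rural item in 6.5.5.
- The SAP interval is the Miettinen-Nurminen score interval.

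**Step 1: the plan's own figure**
- Standard error at 80% v 80%: sqrt(2 x 0.8 x 0.2 / 260) = 0.03508.
- The rates constrained to differ by 10 points are 74.1% and 84.1%, giving sqrt((0.741 x 0.259 + 0.841 x 0.159) / 260) = 0.03539.
- Power = Phi((0.10 - 1.96 x 0.03539) / 0.03508) = Phi(0.873) = 80.9%. The stated figure is reproduced.
- Exact binomial enumeration of the score interval gives 81.2%, and a one-sided error of 2.5% at 70% v 80%.

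**Step 2: the bias formula**

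Let u1 and u2 be the rates in the lower-seropositivity area, g the gap between areas, and r1 and r2 the shares of each dose group in the higher area. Then p1 - p2 = (u1 + r1 g) - (u2 + r2 g) = (u1 - u2) + (r1 - r2) g. The crude difference is therefore off by (r1 - r2) x g. The assumed ranges give 0.10 x 0.05 = 0.5 points up to 0.30 x 0.15 = 4.5 points. The sign is that of (r1 - r2).

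**Step 3: effect on the criterion**

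Exact enumeration, 260 per group, 2-dose rate 80%:

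| Shift (points) | Example: imbalance x gap | Chance of passing at true -10, shift favours 1 dose | Power at true equality, shift against 1 dose |
|---|---|---|---|
| 0 | none | 2.5% | 81.2% |
| 0.5 | 10 x 5 | 3.4% | 76.7% |
| 1 | 10 x 10 | 4.5% | 71.8% |
| 2 | 20 x 10 | 7.7% | 60.9% |
| 3 | 30 x 10 | 12.5% | 49.2% |
| 4.5 | 30 x 15 | 23.1% | 32.5% |

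A shift of about 1.2 points doubles the 2.5% error to 5%. For scale, with 208/260 seropositive after two doses, 201/260 after one dose passes (difference -2.7, lower limit -9.8) and 200/260 fails (difference -3.1, lower limit -10.2). A 2-point shift is large against that room.

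**Step 4: cost of stratifying**

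This uses a normal approximation with equal schedules, Mantel-Haenszel weights, half of all children in each area and an average rate of 80%. For a 20-point gap and 40-point imbalance (shares 70% and 30%, rates 90% and 70%), each stratum has weight 0.5. The variance is 0.25 x (0.09 + 0.21) x (1/182 + 1/78) = 0.001374, so the standard error is 0.03706 and power = Phi(0.10/0.03706 - 1.96) = 77.0%. The same steps give 80.4% (gap 10, imbalance 20) and 82.2% (gap 20, imbalance 20), against 81.3% with no residence effect.

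**The case against.** **Direction and size are not documented.** A reader might infer that natural exposure will push this study towards non-inferiority. The documents do not support that. They give no rural/urban figures for exposure or for second-dose completion; the completion figures in protocol 1.1 differ by calendar year (11% in 2007, 65% in 2008), not by place. The opposite imbalance would hide real non-inferiority. At the smallest assumed shift the error is 3.4% against 2.5%, which is minor. This stands: the calculation shows what a shift would do, not that one exists.

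**The plan has partial safeguards.** Known hepatitis A infection is excluded at entry and from the ATP cohort (protocol 5.3 and 8.3.3). SAP section 9 plans a sensitivity analysis without very high titres if natural infection is suspected. SAP 6.1 tabulates residence by dose group, so an imbalance would be seen. These help only in part. Unrecognised infection is not excluded, the section 9 analysis is conditional and misses ordinary titres above the cut-off, and a table of residence corrects nothing.

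**The comparison is exploratory.** Protocol 8.7 says no conclusions can be drawn, and both documents call all analyses descriptive. The primary objective, persistence within each dose group, is unaffected. This limits the consequence, although the SAP 6.2 wording on demonstrating non-inferiority sits badly with it.

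**Residence is a coarse proxy.** One urban/rural item recorded at the visit cannot capture lifetime exposure, and other confounding would remain. True, but it is already collected, and area of residence is the covariate the protocol itself chose.

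**Conclusion.** The concern holds in a two-directional form. The difference set against -10% is crude although the groups are not randomised. The protocol adjusts only the GMC ratio for residence, and the SAP removes that adjustment without listing it. Any bias equals the residence imbalance multiplied by the residence gap in seropositivity, and both are unknown.

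Under assumed shifts of 0.5 to 4.5 points in favour of one dose, the chance of passing at a true -10 points is about 3.4% to 23% rather than 2.5%. A 2-point shift the other way lowers power at equal 80% rates from 81.2% to 60.9%. These figures rest on 260 per group, an 80% 2-dose rate and a gap common to both dose groups.

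Nor should a reader infer that the sample size is wrong: the 80.9% reproduces and simply contains no residence term. The unlisted removal of residence from the GMC model needs no assumption; it follows from protocol 8.6 set beside SAP 7.1 and section 9.

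**What to change.** - In SAP 6.2 and 7.1, compute the difference set against -10% as a Miettinen-Nurminen score difference stratified by urban/rural residence with Mantel-Haenszel weights. Report the crude difference beside it.
- Restore area of residence in the SAP ANOVA for the GMC ratio, as protocol 8.6 states.
- List the change to the seropositivity analysis in SAP section 9, since it departs from protocol 8.6, and describe it in the study report as protocol 8.8 requires.
- Do not stratify further by age class at first dose. It does not address residence, and the open-ended six-month classes in SAP section 2 may be sparse.

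**Cost.** No new data, and one extra table per survey. Precision falls slightly if residence is badly unbalanced: power is about 77% in the extreme assumed case, below the protocol's 80%, and about 80% to 82% in the milder ones. Stratifying removes only the part of any bias that runs through urban/rural residence.
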